1.0 Background

Type 1 diabetes mellitus (T1DM) is an autoimmune condition caused by destruction of the β cells in the pancreas that produce insulin. Current regimens for treating T1DM in clinical practice are mainly based on multiple daily injections of subcutaneous insulin in dosages determined by intermittent blood glucose measurements. Continuous subcutaneous insulin infusion (CSII) via a pump provides an alternative form of insulin therapy with the advantage of delivering variable basal rates throughout the day and fewer injections. However, a significant proportion of people with T1DM on current insulin regimens do not achieve optimal blood glucose control which increases the risk of complications including kidney failure, blindness, nerve damage and heart disease. Intensive treatment can lower this risk but may lead to potentially dangerous low blood glucose levels (hypoglycaemia). The Diabetes Control and Complications Trial demonstrated that intensive management reduced complications by 50-76% (1). This was at the expense of increased hypoglycaemia, especially at HbA1c levels <58mmol/mol (7.5%). Severe or prolonged hypoglycaemia is a major concern and can result in seizures, cardiac arrhythmias and is associated with the "dead-in-bed" syndrome (2, 3). Diabetes technologies, such as insulin pumps, bolus calculators, continuous glucose monitors and closed-loop insulin delivery systems, are important in aiding self-management and optimising glycaemic control in type 1 diabetes.

A closed-loop insulin delivery system, also known as an artificial pancreas, provides the potential to improve HbA1c while avoiding hypoglycaemia. It requires continuous glucose measurement by a subcutaneous continuous glucose sensor, a control algorithm and a pump for insulin delivery. Three main control algorithms (proportional-integral-derivative,

model predictive control and MD-logic) have been employed in out-of-clinic closed-loop clinical studies to date (4). Most closed-loop systems utilise insulin alone (5-7), while some groups use a bi-hormonal (insulin and glucagon) approach (8-9).

To support mealtime insulin dosing, people with type 1 diabetes use bolus calculators to provide insulin dose recommendations. A standard bolus calculator uses a generic formula taking into account the target glucose level, current glucose level, carbohydrate content of meal (grams), insulin: carbohydrate ratio (the amount of carbohydrate (grams) covered by 1 unit of insulin), insulin sensitivity factor (the reduction in blood glucose by 1 unit of insulin) and insulin-on-board (IOB, the remaining active insulin from the previous bolus). Some bolus calculators additionally consider parameters such as exercise, but all lack the ability to automatically adapt over time to respond to individual needs. Standard bolus calculators have been incorporated into insulin pumps and some glucose meters.

The Bio-inspired Artificial Pancreas

The diabetes technology group at Imperial College have developed a bio-inspired artificial pancreas (BiAP) system which uses a control algorithm based on a mathematical model of beta-cell behaviour derived from physiological experiments, carried out by other groups, which have demonstrated how the beta cells in the pancreas produce insulin in people without diabetes. Utilising the data from these experiments it has been possible to implement the behaviour of the beta cell in software (10-12) and we have used a simulator with 200 virtual patients to demonstrate the safety and efficacy of the algorithm. The data from the simulator have previously been published (13). The simulator was developed from human data and takes into account glucose-insulin regulation, sensor errors, sensor placement, route of insulin administration and meal-time glucose absorption. It has been approved by the FDA in the United States as a step in the pathway of developing an artificial pancreas and has been validated against human data (14). The BiAP algorithm is implemented on a miniature silicon microchip within a portable handheld device, which interfaces the components of the artificial pancreas.

Clinical evaluation of the BiAP

The existing bio-inspired artificial pancreas has already been evaluated in participants with T1DM during fasting conditions, overnight and following a standard meal (breakfast) challenge and the data have shown good glycaemic control with minimal hypo- or hyperglycaemic excursions (15). Following the feasibility studies, a 24-hour randomised control clinical trial demonstrated that the BiAP system significantly reduces hypoglycaemia

compared to standard insulin pump therapy (16). We have additionally shown that the BiAP remains safe in the event that a meal is unannounced or the carbohydrate content is underestimated (16).

The BiAP system has also been evaluated in standard exercise studies with insulin only artificial pancreas control, insulin and glucagon artificial pancreas control and open-loop insulin pump therapy. These have demonstrated that the controller is able to manage the challenge of prolonged aerobic exercise and that the addition of glucagon does not impact on the risk of hypoglycaemia with physical activity, immediately after physical activity or up to 16 hours after (17, 18)

The Advanced Bolus Calculator for Diabetes

The Imperial College Diabetes Technology team have developed an Advanced Bolus Calculator for Diabetes (ABC4D), a novel, adaptive decision support algorithm based on case-based reasoning (CBR) providing real-time insulin advice through a smartphone application. CBR is an artificial intelligence technique that solves newly encountered problems by applying the solutions learned from solving similar problems encountered in the past. ABC4D utilizes CBR where cases within a case-base are used to represent various meal scenarios (e.g. dinner after exercise). Each time a user requests a new insulin bolus recommendation, the current meal scenario is compared to all existing cases from the past. If a similar case is found the solution of this case is applied to calculate the insulin dose. If no similar case exists, then a new case is created. The outcome of each insulin advice is then revised by analysing the post-prandial glucose excursion provided by continuous glucose monitoring (CGM) data. The ABC4D algorithm has been validated in-silico using the FDA-accepted UVa-Padova type 1 diabetes simulator (19).

Clinical evaluation of the ABC4D

The safety and feasibility of the ABC4D has been evaluated pilot clinical study over 6 weeks in 10 adult participants with T1DM. The clinical outcomes from the pilot study showed that ABC4D is safe and maintains glycaemic control with a trend suggesting improvement in post-prandial hypoglycaemia and overall glucose outcomes (20). A separate analysis of the case parameters used in ABC4D showed that the alcohol and exercise parameters were most frequently used suggesting a clinical benefit in terms of improving post-prandial hypoglycaemia (21). The usability and acceptability of the system architecture was favourable with 8 out of 10 users trusting the advice generated and 9 out of 10 happy to use ABC4D (22). A powered randomised controlled trial over 6 months is currently underway to assess whether the ABC4D system is superior to a non-adaptive bolus calculator.

The components of the closed-loop insulin delivery system

The complete device used in this protocol comprises a commercial continuous subcutaneous glucose sensor (Dexcom G5 CGM system), the BiAP control algorithm implemented in a low-power handheld device (developed by the Imperial Diabetes Technology team), the ABC4D adaptive bolus calculator algorithm in a smartphone platform (developed by the Imperial Diabetes Technology team) and a commercial continuous subcutaneous infusion pumps (Tandem T-slim) to provide glucose control. Fig 1 gives an overview of the complete system architecture. If participants already have intraperitoneal (IP) access (DiaPort) then the insulin will be delivered via the intraperitoneal route in accordance with these participants' standard care.

Glucose sensor

The glucose sensor that will be used throughout the clinical validation studies is a CE marked and MHRA approved device commercially available (Dexcom G5 Mobile CGM system). Subcutaneous sensors sit just under the skin and sample interstitial fluid using an enzyme electrode. A small voltage is applied across the sensor and a current is fed back to the sensor instrumentation. This current is proportional to the glucose concentration in interstitial fluid and is calibrated against blood glucose a minimum of 12 hourly.

BiAP algorithm in a low-power handheld device As outlined above

ABC4D adaptive bolus calculator algorithm in a smartphone platform As outlined above

Insulin infusion pump

The pump is a small (6cm x 4cm) device, containing a cartridge that can be filled with insulin, which delivers a continuous infusion of insulin into the subcutaneous (fat) tissue or intraperitoneal space via a tube connected to a pump cannula. The pump device used throughout the clinical validation is the Tandem t:slim which is FDA-approved and commercially available in the United States for use with Insulin Aspart (Novorapid) and Insulin Lispro (Humalog). The insulin pump is not CE-marked and not commercially available in Europe at present and will be labelled "exclusively for clinical investigations". Participants will continue on their usual insulin, but the insulins used will be restricted to Insulin Aspart (Novorapid) and Insulin Lispro (Humalog).

Fig 1. System architecture

Glucose data from the Dexcom G5 transmitter are sent by Bluetooth LE to the BiAP handheld unit where the bio-inspired algorithm is operating and insulin microbolus data are sent on to the Tandem t:slim pump at appropriate intervals (e.g. 5 minutes). At mealtimes (any meal or snack containing 15g or more of carbohydrate), the study participants will inform the smartphone of a meal and enter a carbohydrate estimate before eating. The pump will deliver a bolus calculated either according to a fixed or adaptive algorithm. The controller and smartphone will, at all times, know insulin-on-board, ensuring safety. Data will be fed by wifi or cellular data (3G/4G) to the research team but will not be monitored in real-time.

Safety

Remote monitoring will not be routinely used but all participants will have 24-hour access to engineering and clinical support and will have a clear written plan in case of technical challenges. The facility to share data in real-time will be provided on the handset using Bluetooth to mirror data on the smartphone device with WiFi or 3G communication, to enable the support team to provide timely and appropriate advice.

To ensure participant safety, individualised constraints based on patient specific parameters (insulin:carbohydrate ratio, insulin sensitivity factor and insulin-on-board) are applied to the insulin calculated by the controller. Hypoglycaemia prevention strategies including insulin infusion reduction and suspension are employed for forecasted glucose concentrations below predefined thresholds. An alarm system alerting for device communication errors, sensor failures, hyper- and hypoglycaemia is in place and in case of sensor or controller failure insulin infusion will revert to a safe basal rate (% of a pre-programmed optimum). Finally, remote monitoring of RT-CGM, reflecting artificial pancreas functioning, will be available to the study team using a CE marked smartphone application (Dexcom Follow App). The study team will not be monitoring the data continuously, but will be able to use this information if participants seek technical/clinical support.

Potential risks and benefits

The potential risks and burdens for research participants are as follows:

Some visits involve taking a venous blood test. These have the potential to cause discomfort. This will be minimised by experienced research personnel and appropriate use of equipment.

Throughout the study, participants will have a subcutaneous insulin infusion pump cannula inserted and these need to be replaced every 3 days. All participants will use subcutaneous insulin infusion pumps for routine care. Participants will also have the glucose sensor inserted and these need to be changed every 7 days. Both pump cannula and glucose sensor insertion can be associated with some discomfort but the insertion devices are spring-loaded with introducers, making the process rapid and often painless. Any discomfort will be minimised by adhering to manufacturer's instructions.

During the closed-loop study periods there is a risk from the new technology. The controller may suggest an excess or relatively deficiency of insulin infusion. Participants will be advised to check their capillary blood glucose as per routine care and in addition they will have access to real-time CGM. glucose values are frequently monitored to prevent adverse events related to elevated or low glucose values. To date the BiAP system and the ABC4D system have been evaluated in clinical studies in participants with T1DM without incidents of severe hypo- or hyperglycaemic excursions.

It is well-known that insulin requirements change during pregnancy and hence participants who are female and of childbearing age will have a urine pregnancy test done at screening and prior to each intervention. Participants will be excluded from the study if they are pregnant or planning pregnancy within the study time frame, to minimise any potential risk.

It is acknowledged that the clinical schedule is demanding of subject's time and includes overnight visits. This inconvenience is necessary to adequately and safely ensure participants receive the appropriate training on how to use the device and we will minimise the burden as much as possible by providing entertainment (TV, radio, reading material, internet access) in a comfortable environment with privacy. We will also ensure to make every effort to schedule visits around participants' lifestyles.

Research participants will benefit from being in the study by having increased access to diabetes professionals and more frequent visits to hospital with an emphasis on improved glycaemic control. They will also have the opportunity to use continuous glucose monitoring and review the results with a consultant diabetologist experienced with monitoring. The benefits to people with T1DM include the potential to carry forward technology to improve the risks of high glucose concentration leading to complications and distressing low glucose values.

Route of administration, dosage, dosage regimen, and treatment period

Insulin will be administered subcutaneously or intraperitoneally (in those who already have IP access with a DiaPort). This is the standard route of administration for insulin in T1DM. Alternative routes of administration include intravenous or inhaled. Intravenous insulin is used clinically in people with diabetes who are acutely unwell or those unable to eat and drink, inhaled insulin is no longer commercially available in the UK. The insulin dosage will be expressed as units infused subcutaneously as microboluses and will be calculated by the control algorithm of the closed-loop at 5-minute intervals. The treatment periods are defined by time spent in closed-loop insulin delivery.

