2.0 Clinical study

The trial will be conducted in compliance with the protocol, GCP and the applicable regulatory requirement(s).

Trial Objectives and Purpose

The main objectives of the research study is to evaluate the safety, efficacy and costeffectiveness of a bio-inspired artificial pancreas (BiAP) with, and without, the addition of an adaptive bolus calculator (ABC4D) compared to gold-standard sensor-augmented pump therapy.

Hypothesis

- 1. A bio-inspired artificial pancreas (BiAP) device has a positive impact on glucose control, as measured by time in target after 6 weeks of use, when compared with sensor-augmented pump with low-glucose suspend (LGS).
- 2. A bio-inspired artificial pancreas (BiAP) device with an adaptive bolus controller (ABC4D) has an additional positive impact on post-prandial glucose control.

Trial Design

A 3-way crossover randomized controlled trial (Fig 3). Description of the three arms:

- 1. Sensor augmented pump (open-loop)
- 2. BiAP with a fixed bolus calculator
- 3. BiAP with the Advanced Bolus Calculator for Diabetes (ABC4D)

The primary outcome from the studies will be % time spent with a glucose concentration in the target range (3.9-10.0mmol/l). This outcome incorporates safety as it ensures participants do not have low or high glucose excursions and is the principal measure of efficacy for closed-loop insulin delivery systems in the scientific literature. Other measured outcomes will be % time spent in euglycaemia (3.9-7.8mmol/l), % time spent in hypoglycaemia (<3.9mmol/l), % time spent in hyperglycaemia (>10mmol/l), mean venous blood and sensor glucose, glycaemic variability as measured by standard metrics (SD, CONGA, LI, JINDEX, GRADE, MODD, MAGE, ADDR, MVALUE, MAG), glycaemic risk as measured by low blood glucose index (LBGI) and high blood glucose index (HBGI), closed-loop error grid analysis, glucose area under the curve. All measures have been previously published and validated. Quality of life, treatment satisfaction and device acceptability outcomes will be measured using mixed methods (questionnaires and semi-structured interviews).

Methodology Randomised controlled cross-over open label study

Timescale It is anticipated that the study will take 1 year, each subject will be in the study for up 6 months, with a total of 6 visits in that timeframe.

Population

n = 20

Inclusion criteria

- Adults over 18 years of age

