- They will be free to go home at 18:00 with the BiAP device to continue the remaining 6 weeks.
- Participants will be trained to use the sensor, controller and insulin pump.
- They will have a structured education refresher.
- All training will be delivered by the study team and will be supported with written information. Participants will be expected to be able to self-manage the sensor, controller and pump prior to leaving the clinical research facility and competencies will be clearly recorded. Videos to support sensor insertion, and pump cannula and reservoir operations will be provided to all participants via email or on a USB stick and can be uploaded to participants' smartphones for off-line use. Contact details for clinical and technical support will be provided.
- The study team will phone the participants on day 1, day 3, day 7 and at 3 weeks.

Visit 4: End of first 6-week intervention period

- Attend the clinical research facility.
- Review any issues with the technology used.
- Download data from the study pump (the pump stores data for 90 days).
- Provide consumables (sensors, transmitter, insulin infusion sets) for the next 6-week intervention period.
- Gold score
- Mixed methods psychological assessment: Diabetes quality of life (DQOL), Diabetes Treatment Satisfaction Questionnaire (DTSQ) and PAID Questionnaire to be completed. Semi-structured interviews by the investigators will be carried out.
- Acceptability questionnaire to be completed.
- Repeat urine pregnancy test in female participants of childbearing age

• Participants will be instructed to revert back to their usual care for 2 weeks (wash-out period) before commencing the next intervention for 6 weeks.

Visit 5: End of 2nd 6-week intervention period

- Attend the clinical research facility.
- Review any issues with the technology used.
- Download data from the study pump.
- Provide consumables (sensors, transmitter, insulin infusion sets) for the next 6-week intervention period.
- Gold score
- Mixed methods psychological assessment: Diabetes quality of life (DQOL), Diabetes Treatment Satisfaction Questionnaire (DTSQ) and PAID Questionnaire to be completed. Semi-structured interviews by the investigators will be carried out.
- Acceptability questionnaire to be completed.
- Repeat urine pregnancy test in female participants of childbearing age

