- Participants will be instructed to revert back to their usual care for 2 weeks (wash-out period) before commencing the next intervention for 6 weeks.

Visit 6: End of 3rd 6-week intervention period and end of study

- Attend the clinical research facility.
- Review any issues with the technology used.
- Gold score
- Mixed methods psychological assessment: Diabetes quality of life (DQOL), Diabetes Treatment Satisfaction Questionnaire (DTSQ) and PAID Questionnaire to be completed. Semi-structured interviews by the investigators will be carried out.
- Acceptability questionnaire to be completed.
- Participants will be asked to return all components of the study device and will be instructed to revert back to their usual care.

Activity / Visit no	1	2	3	4	5	6	Additional information
Insertion of CGM sensor	X						Participants will change the sensor every week at home throughout the study
CGM review with participant		х					
Randomisation + Initialise the			Х	Х	Х		

Table: Overview of activities at each visit for participants

intervention/control							
Update CBR algorithm with new							This will be done automatically in
cases							the BiAP+ABC4D intervention
Clinical examination	x						
Weight measurement	x						
Venous blood test	Х						
Urine test	Х			Х	Х		
Pregnancy test (if applicable)	Х						
ECG	Х						
Questionnaire/s	Х			Х	Х	Х	
Follow-up clinical visits		Х	Х	Х	Х	Х	
Overnight stay in clinical			х				
research facility							
Semi-structured interview	Х			х	х	х	

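### Self-reported outcomes are collected open label, after the technology review and partly after the investigator interview; questionnaires should be self-completed first

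*Combined protocol and SAP*

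**What the plan says.** Under Methodology in section 2.0 the trial is a "Randomised controlled cross-over open label study". Trial Design lists three arms: sensor-augmented pump, "BiAP with a fixed bolus calculator", and BiAP with ABC4D. No section describes masking between the two BiAP arms or gives a reason for its absence.

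The system description in section 1.0 gives one meal-time procedure: "the study participants will inform the smartphone of a meal and enter a carbohydrate estimate before eating". It continues: "The pump will deliver a bolus calculated either according to a fixed or adaptive algorithm". The table of visit activities says of updating the ABC4D case base: "This will be done automatically in" the combined BiAP and ABC4D intervention.

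Visits 4, 5 and 6 each list, near the top, "Review any issues with the technology used". Further down comes one item naming DQOL, DTSQ and PAID, which ends "Semi-structured interviews by the investigators will be carried out". The acceptability questionnaire is a separate item after that.

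Section 3.0 includes quality of life, and device usability and acceptability, among the secondary outcomes. Section 1.0 says that groups at Imperial College, the sponsor, developed both BiAP and ABC4D.

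**The concern.** In an open-label crossover each participant rates three treatments in turn, and the within-person differences in those ratings are the result. Two things can move the ratings apart from the treatment itself. One is expectation: a person who knows that the calculator adapts may trust it more and score it higher. The other is the conversation that comes first. A discussion of what went wrong with the equipment, or an interview by a member of the team that built it, can colour the answers that follow.

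DQOL, DTSQ, PAID and acceptability are directly exposed because the measurement is the participant's own judgement. CGM time in range is measured by a device and is less exposed, but it still depends on behaviour such as announcing meals, estimating carbohydrate and choosing to stay in closed loop. At stake is whether a difference in satisfaction or acceptability between arms can be credited to the system.

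**Working it through.** **Order of tasks.** Item positions in the visit lists of section 2.0:

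| Task | Visit 4 | Visit 5 | Visit 6 |
|---|---|---|---|
| Technology review | 2 | 2 | 2 |
| Pump data download | 3 | 3 | not listed |
| DQOL, DTSQ, PAID, then interview (one item) | 6 | 6 | 4 |
| Acceptability questionnaire | 7 | 7 | 5 |

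At all three visits the technology review precedes all four questionnaires. The interview precedes only the acceptability questionnaire; DQOL, DTSQ and PAID are named before the interview within their shared item. The documents do not say who hands out the questionnaires or whether participants complete them alone.

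**Size for self-report.** The documents give no SD, margin or expected difference for any questionnaire, so no figure can be computed.

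**Size for time in range (illustration).** The plan states no figure for expectation bias, so there is none to reproduce. Inputs from section 3.0 are n = 20, SD 9.9, three pairwise comparisons and a 5% level corrected for multiplicity. Assumed here: Bonferroni (0.05/3 = 0.0167, two-sided), no true effect, and a pure expectation shift b of 1, 2 or 3 points.

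Section 3.0 does not say whether 9.9 is the SD of paired differences or a per-arm SD. The stated sample size does not settle this. With 12 points and 90% power, the normal approximation (z values 2.394 and 1.282, sum squared about 13.51) gives:
- Difference SD 9.9: 9.9² × 13.51 / 12² = 9.2, so 10 participants (13 by exact t).
- Per-arm SD 9.9, zero correlation: 2 × 9.9² × 13.51 / 12² = 18.4, so 19 participants (22 by exact t). This is near the planned 20.

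Both readings are therefore carried forward. SE = SD/√20, noncentrality λ = b/SE, and the rejection rate is the probability that |T| exceeds 2.625, with T noncentral t on 19 df.

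| Shift b | SD 9.9, SE 2.214: λ | Rejection | SD 9.9√2 = 14.0, SE 3.131: λ | Rejection |
|---|---|---|---|---|
| 0 | 0 | 1.7% | 0 | 1.7% |
| 1 | 0.452 | 2.7% | 0.319 | 2.2% |
| 2 | 0.903 | 6.0% | 0.639 | 3.7% |
| 3 | 1.355 | 12.8% | 0.958 | 6.7% |

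Section 3.0 anticipates 6 points for ABC4D over fixed bolus, so a 3-point shift would be half of it (3/6) and a 2-point shift one third (2/6). Nothing in the documents says that a shift of any of these sizes occurs, or in which direction.

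**The case against.** The strongest reply on the questionnaires is that the visit items are not stated to be a sequence. Sites may already hand out the forms first, and three of the four instruments are named before the interview. That stands: the lists do not prove that the questionnaires come last. But no text prevents it either, and the order matters enough to be written down.

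A second reply is that reordering cannot remove expectation, because participants will still know their treatment. That also stands. The change limits the influence of the preceding conversation and no more.

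A reader might infer something stronger: that the two BiAP arms differ only by a software switch, that participants are told its position, and that masking would therefore have avoided the bias. The documents do not support this.
- The sentence about fixed or adaptive boluses does not say what participants are told. That follows only from the open-label description.
- Section 1.0 describes ABC4D as matching meal scenarios, and reports alcohol and exercise parameters as the most used in its pilot. Whether the fixed arm has the same screens and fields is not stated.
- Participants are experienced pump users whose ratios are reviewed with them at Visit 2, and each uses both calculators. If doses are displayed, many could work out which is active.
- Masking would place inactive fields in the comparator and withhold the active dosing algorithm from staff making the support calls during home use.

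Finally, the illustration concerns time in range, whereas Hypothesis 2 is worded as post-prandial control, for which section 3.0 gives no effect or SD.

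**Conclusion.** The point holds for the self-reported secondary outcomes. The trial is open label between all arms, the plan does not place the questionnaires ahead of the technology review, and it lists the acceptability questionnaire after the investigator interview. These outcomes are open to expectation and interviewer influence, and part of that influence can be removed at no cost.

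The size is unknown, both for the questionnaires and for CGM time in range. The rejection rates of 2.7%, 6.0% and 12.8% (or 2.2%, 3.7% and 6.7%) rest on assumed shifts, an assumed Bonferroni correction and one of two readings of the SD. They show sensitivity and are not an estimate of bias.

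The documents do not establish that leaving fixed versus adaptive bolus unmasked is an avoidable defect. Masking there is a design option with real trade-offs. The point does not extend to masking BiAP against sensor-augmented pump, where open-loop and closed-loop use are visibly different.

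**What to change.** Add to the descriptions of Visits 4, 5 and 6, for every arm:

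> On arrival, and before the technology review, any data download and the semi-structured interview, the participant completes the DQOL, DTSQ, PAID and acceptability questionnaires without assistance from the study team.

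The cost is the order of tasks at three visits, with no added procedure or visit time. In reporting, describe these outcomes as open label.

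Optionally, add a sentence saying whether masking of fixed versus adaptive bolus within the BiAP periods was considered and why it was or was not adopted. Adopting it would need identical screens and inputs in both periods, and a decision by the sponsor on how the support staff's need to know the active algorithm would be met. The reordering does not depend on that decision.
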